3.5.6 Exposure (vaccination)

Definition

For vaccinations requiring one dose (seasonal or pandemic vaccination)

An individual is considered vaccinated 14 days after vaccination is performed.

For children, for seasonal flu vaccination

- A child is considered fully vaccinated:
 - 14 days after he/she had two influenza shots; or
 - 14 days after receipt of one influenza shot and was vaccinated in the previous year
- A child is considered partially vaccinated 14 days after receipt of one influenza shot in absence of vaccination the year before.

For pandemic vaccination requiring two doses:

If two doses of pandemic vaccine are required, the terms 'fully' and 'partially' vaccinated should be defined and applied.

Ascertainment

An individual will be considered as vaccinated against influenza if:

- he or she is registered as vaccinated in a vaccination registry;
- he or she reports having received influenza vaccination during the current season; or
- his or her insurance company can show evidence of pharmacy delivery or re-imbursement of influenza vaccination in the current influenza season.
- ☑ The precise mode of vaccine ascertainment in each study should be specified in study annexes.

The exposures of interest in this study are vaccination with pandemic influenza vaccine and trivalent seasonal influenza vaccine. The history of vaccination will include date of administration, type of vaccine (seasonal or pandemic), number of doses and brand name.

The investigation team must identify brands used in the area and compile a list of possible brands used.

3.5.7 Risk groups

Pandemic vaccine

According to ECDC interim guidance³, the risk groups to be considered for the pandemic vaccine are:

- people aged less than 65 years with chronic underlying conditions, namely:
 - chronic respiratory diseases;
 - chronic cardiovascular diseases;
 - chronic metabolic disorders (notably diabetes);
 - chronic renal and hepatic diseases;
 - persons with deficient immunity (congenital or acquired);
 - chronic neurological or neuromuscular conditions;
 - any other condition that impairs a person's immunity or prejudices their respiratory function;

http://www.ecdc.europa.eu/en/publications/Publications/Forms/ECDC_DispForm.aspx?ID=388

³ European Centre for Disease Prevention and Control (ECDC). Interim guidance: Use of specific pandemic influenza vaccines during the H1N1 2009 pandemic. Stockholm: ECDC; 2009. Available from:

- young children (especially under the age of two years);
- pregnant women.

Other target groups may include healthcare workers, essential service workers, caregivers of infants < 6 months old

Seasonal vaccine

Individuals are considered to belong to a risk group if their patient record contains any of the ICD codes listed on Table 5 or if they report having one of the underlying conditions included in the same table.

3.5.8 Confounding factors/effect modifiers

To control for differences in vaccinated compared to non-vaccinated individuals, information on potential confounding factors is collected.

The minimum confounding factors to be considered include chronic diseases, indicators of the severity of chronic diseases, current vaccination with seasonal flu vaccination (if IVE of pandemic vaccine is calculated), current vaccination with pandemic flu vaccination (if IVE of seasonal vaccine is calculated), previous influenza vaccination, antiviral drug use, smoking and functional status (the latter if cluster is in elderly people).

Below is a list of confounding factors and effect modifiers. Not all information will be relevant or available given the nature of the cluster.

☑ The precise information collected in each study should be specified in the study annexes.

Chronic diseases

An individual will be classified as belonging to a high risk group if:

- medical records indicate presence of chronic disease (see Table 5)
- he/she reports having the following underlying conditions:
 - diabetes if treated for insulin-dependent or non-insulin-dependent diabetes;
 - cardiovascular disease if has had any of the following: myocardial infarction, angioplasty, coronary artery bypass surgery, stroke, transient ischaemic attacks, treated hypercholesterolaemia, treated hypertension;
 - chronic pulmonary disease;
 - immunodeficiency.

Table 5: ICD and ICHPPC-2 codes for chronic diseases

Chronic diseases	ICD Code	ICHPPC-2 code
Anaemia spleen	280–289 and 759.0	B82
Cirrhosis	571	D97
Diabetes and endocrine	250 and 251	T89 and T90
Heart disease	093, 112.81, 130.3, 391, 393–398, 402, 404, 410–429, 745, 746, 747.1, 747.49, 759.82, 785.2, and 785.3	K71, K74-77, K81-K84, K86-K87 and K99
Haematologic cancer	200–208	B72 andB74
Immunodeficiency and organ transplant	042, 079, 279, V08, and V42	B99
Lung disease	011, 460, 462, 465, 466, 480–511, 512.8, 513–517, 518.3, 518.8, 519.9, and 714.81	A70, R83, R79, R95, R96 and R99
Non-haematologic cancer	140–198 and 199.1	A79, D74-D78, F74, H75, K72, L71, N74, N76, R84, R85, S77, S79, T71, T73, U75-U77, U79, W72-W73, X75-X77, X81 and Y77-Y
Nutritional deficiencies	254, 255, 259.2, and 260–269	T05 and T99
Renal disease	274.1, 408, 580–591, 593.71–593.73, and 593.9	U99
Dementia, stroke	290-294, 331, 340, 341, 348, and 438	P70 and K90
Rheumatologic diseases	446, 710, 714.0–714.4, 714.8, 714.89, and 714.9	L88

☐ The precise codes used in each study should be specified in study annexes.

Severity

The severity of the underlying conditions will be measured by the number of hospital admissions due to the underlying conditions in the year prior to study inclusion.

Smoking history

Smoking history will be collected and coded as 'never smoked', 'former smoker' (stopped smoking at least one year before inclusion in the study) and 'current smoker'.

Former vaccination

Former vaccination includes:

 Vaccination against influenza in the previous two years (collecting information on vaccination for each of the seasons).

Functional status (where applicable)

Information on functional status will be collected in terms of needing assistance with bathing.

Antiviral administration

Use of antivirals will be documented: type, dose and date of administration.

Other confounding factors that should be considered if available or relevant include:

- Level of social interaction
 - Number of household members
 - Children: nursery vs. school-age children
- Indicators of socio-economic status
 - Education level
 - Profession
 - Others (e.g. deprivation score by area of residence)
- Any other available and relevant for the study population

3.5.8 Sample size

In a cluster investigation the number of cases available is often fixed, which limits the power of the study. Prior to the beginning of the study, calculations to determine the power of the study for detecting a given measure of effect with a set number of cases can be useful. This can also help determine if the control-to-case ratio needs to be increased to give more power.

Table 6 illustrates the various sample sizes that would ensure an alpha error of 0.05, a power of 0.8 or 0.9, a detectable odds ratio ranging from 0.3 to 0.6, and a vaccine coverage among the source population (or among controls) ranging from 50% to 70%.

The sample size should be respected for each population subgroup in which a sub- (stratified) analysis (e.g. effect modification) is planned.

Table 6: Sample size calculations

Power	Alpha	Controls/case	Vaccine coverage in source population/ controls	Detectable OR	Number of cases	Number of controls
0.90	0.05	1	50%	0.6	345	345
0.80	0.05	1	50%	0.6	262	262
0.90	0.05	1	50%	0.5	194	194
0.80	0.05	1	50%	0.5	148	148
0.90	0.05	1	50%	0.4	116	116
0.80	0.05	1	50%	0.4	89	89
0.90	0.05	1	50%	0.3	72	72
0.80	0.05	1	50%	0.3	56	56
0.90	0.05	1	60%	0.6	341	341
0.80	0.05	1	60%	0.6	259	259

Power	Alpha	Controls/case	Vaccine coverage in source population/ controls	Detectable OR	Number of cases	Number of controls
0.90	0.05	1	60%	0.5	188	188
0.80	0.05	1	60%	0.5	144	144
0.90	0.05	1	60%	0.4	110	110
0.80	0.05	1	60%	0.4	85	85
0.90	0.05	1	60%	0.3	67	67
0.80	0.05	1	60%	0.3	52	52
0.90	0.05	1	70%	0.6	370	370
0.80	0.05	1	70%	0.6	281	281
0.90	0.05	1	70%	0.5	200	200
0.80	0.05	1	70%	0.5	153	153
0.90	0.05	1	70%	0.4	115	115
0.80	0.05	1	70%	0.4	89	89
0.90	0.05	1	70%	0.3	68	68
0.80	0.05	1	70%	0.3	53	53

3.5.10 Data

Data collection

Data will be collected from all study participants using a standardised questionnaire. The procedures to collect data should be defined by each study coordinator (e.g. face-to-face, by telephone, postal questionnaire, webbased, etc.).

Double data entry is needed.

Details on data collection methods, data entry and data transmission should be specified in study annexes.

Information collected

(see Annex)

- Study participant demographics
- Signs, symptoms
- Severity: hospitalisation, pneumonia, death
- Date of onset of symptoms
- Date of swabbing
- Laboratory results
- Selected underlying chronic conditions
- Number of hospitalisations in the previous year (if relevant)
- Number of GP visits in the previous year (if relevant)
- Smoking history
- Current influenza vaccination(s) including date of vaccination, doses, type (seasonal, pandemic) and brand (if possible)
- Former influenza vaccination
- Functional status (if relevant)
- Pregnant: yes/no (if relevant)
- Use of antivirals, type, dose and date of administration
- Information on respiratory symptoms or laboratory-confirmed A(H1N1) influenza since the beginning of the pandemic in their country (or other date according to the duration of the pandemic) and prior to the cluster/outbreak

Data validation

If data are collected using paper questionnaires, a sample of paper questionnaires will be checked against the study database to validate data entry.

The specific validations procedures should be specified in study annexes.

Data cleaning

Summary and frequency tables and graphic displays of appropriate variables will be used to find illegal, implausible or missing values within the dataset. Checks for inconsistencies will be carried out (e.g. date of swabbing before date of onset of symptoms). These values will be checked against the questionnaires or queried with the study participant. Any changes to the data will be documented and stored separately from the crude database. Any recoding of data (e.g. age from date of birth) will be documented.

3.5.11 Analysis

Analyses will be carried out separately for seasonal and pandemic vaccines and for different vaccine brands.

Separate analyses will be carried out for the different primary and secondary outcomes.

Analyses will be carried out including and excluding persons with recent respiratory symptoms (prior to cluster) that were not lab-confirmed, where information is available.

An analysis will be carried out including only persons 'fully vaccinated' in the vaccinated group. A second analysis will include persons 'fully' and 'partially vaccinated' in the vaccinated group.

Descriptive and univariable analyses

The proportion of eligible ILI cases and controls accepting to participate in the study is calculated (response rate).

Study participants are described by baseline characteristics. Baseline characteristics of cases and controls in unmatched studies are compared using the chi-square test, Fisher's exact test, t-test or the Mann-Whitney test (depending on the nature of the variable and the sample size). In matched case-control studies, characteristics of cases and controls are compared using McNemar's chi-square test, paired t-test, conditional logistic regression or the Wilcoxon signed-rank test (depending on the nature of the variable and the number of controls).

The association between vaccination status and baseline characteristics is assessed for both case and control groups.

Measure of effect

The vaccine effectiveness will be computed as VE = 1 - OR. An exact 95% confidence interval is computed around the point estimate.

Stratified analysis

Analysis will be stratified according to:

- age groups;
- presence or absence of high risk conditions.

A sufficient sample size should be planned in order to ensure sufficient individuals in each stratum. Studies should aim to have at least 80 cases and 80 controls in each of the strata. Effect modification is assessed by comparing the OR across the strata of the baseline characteristics. Confounding is assessed by comparing crude and adjusted OR for each baseline characteristic.

Multivariable analysis

A multivariable (conditional, if matched) logistic regression analysis will be conducted to control for negative and positive confounding. Odds ratios and standard errors will be obtained. Preferably, the model will include: current influenza vaccination, former influenza vaccination, underlying chronic conditions, age, sex and smoking and functional status. Variables will be tested for multicollinearity. Interactions will be tested for using the Likelihood Ratio test (or Wald test) and included in the model if significant at 5% level. Factors other than statistical significance will also be used as criteria for inclusion of an interaction term.

4 Limitations

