3.1 Definition of cluster

A cluster is defined as a group of cases of pandemic influenza (H1N1) 2009 that are related in time and space. Examples include cases in residential care homes, schools, universities, out-of-home childcare settings, healthcare, workplace and household clusters, mass gathering events and outbreaks in cruise ships. Identification of a cluster suitable for measuring vaccine effectiveness – adapted from Orenstein et al¹:

- absence of substantial prior influenza (H1N1) activity in the studied group;
- population containing both vaccinees and non-vaccinees;
- adequate population size in the group to be studied;
- high overall attack rate;
- good vaccination records available to differentiate non-vaccinees from vaccinees.

In addition, the cluster has to be identified early enough to obtain samples within a short delay between onset of symptoms and swabbing (to reduce misclassification of outcome), if laboratory-confirmed outcomes are used.

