- confounding is assessed by comparing crude and adjusted RR for each baseline characteristic.

Multivariable analysis

A multivariable analysis is conducted to control for negative and positive confounding. Variables will be tested for multicollinearity.

The type of multivariable analysis depends on the nature (high or low incidence) of the cluster and the type of denominator used (persons or person-time). Regression methods could include Cox, Poisson or logistic regression.

The multivariable analysis type and model building strategy should be specified in study annexes.

Sensitivity analysis

In order to assess effects of a potential confounding factor not included in the analysis on VE estimates, a sensitivity analysis could be conducted.

Any sensitivity analysis carried out should be specified in study annexes.

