3.5.5 Controls

The selection of controls varies according to the nature of the cluster.

Controls must be representative of the source population from which the cases arise in respect to vaccination coverage. In a traditional case-control study, controls who are still disease free (i.e. who did not have A(H1N1)v infection or other outcome of interest) are chosen at the end of the cluster/outbreak. In a case-cohort study, controls are selected from persons who are disease-free at the beginning of the cluster/outbreak. Therefore, persons who got the outcome of interest during the cluster/outbreak can be included as controls. Control selection among people still free of the outcome of interest when a case arises forms a density case-control study.

Controls can be unmatched or matched to cases.

Selection and characteristics of controls should be listed in study annexes.

Control inclusion criteria

Controls are eligible if they meet the above control definition and accept to participate.

☑ Oral or written informed consent according to country procedures should be specified in the study annexes.

Control exclusion criteria

Controls are excluded if they are not eligible for influenza vaccination because of having a condition listed in the summary of products characteristics (e.g. anaphylactic hypersensitivity to eggs or its components) or if they refuse participation. People with laboratory-confirmed diagnosis of A(H1N1)v infection since the beginning of the pandemic (or other date, according to the duration of the pandemic) and prior to the beginning of the outbreak/cluster of influenza are excluded, as they are not at risk.

People who were not swabbed but had respiratory symptoms in the interval from the beginning of the pandemic (or other date, according to the duration of the pandemic) and prior to the beginning of the outbreak/cluster will be documented and analyses carried out including and excluding them.

Reasons for exclusion must be documented.

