4.6 Overestimation of IVE

If the incidence of A(H1N1)v infections is high in the cluster/outbreak and a traditional case-control study design is used – or a cohort design using logistic regression to obtain ORs – then the IVE may be overestimated.

5 Consent

According to country-specific regulations, informed (oral or written) consent will be required from each participant into the study.

☐ The type of consent (oral/written) should be specified in study annexes.

6 Dissemination of results

Each study team will specify how the results will be disseminated.

Dissemination of results should be specified in study annexes.

7 Logistical aspects

For each cluster investigation, a principal investigator needs to be appointed. For secondary attack rate in household analyses, a system of notification of index cases within households needs to be determined (e.g. sentinel network of GPs).

Computer support needs to be in place.

For each cluster investigation, the study group applies specific criteria to identify the relevant laboratories for RT-PCR, culture and sequencing. Key points to be taken care of include:

- sampling materials;
- transport;
- quality assurance; and
- funding of laboratory tests.

8 Budget

Key components include:

- study team;
- laboratory;
- IT support, programming.
- A detailed budget, specifying which part of the budget will be requested from ECDC, should be outlined in the study annexes.

References

- Centers for Disease Prevention and Control (CDC). Interim within-season estimate of the effectiveness of trivalent inactivated influenza vaccine Marshfield, Wisconsin, 2007–08 influenza season. Morb Mortal Wkly Rep 2008 Apr 18;57(15):393-8.
- Farrington CP. Estimation of vaccine effectiveness using the screening method. Int J Epidemiol 1993 Aug; 22(4):742-6.
- Farrington CP. Re: "The effect of disease prior to an outbreak on estimates of vaccine efficacy following the outbreak". Am J Epidemiol 1996 143(9):961.

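### In the high-attack-rate clusters the protocol seeks, end-of-outbreak controls with VE = 1 - OR, or logistic regression in a cohort, overstate VE relative to 1 - RR; section 4.6 admits this but no rule in the methods avoids it

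*Protocol*

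**What the plan says.** Section 3.1 includes "high overall attack rate" among the criteria for a cluster suitable for measuring VE.

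Section 3.5.5 sets a general rule for controls: "Controls must be representative of the source population from which the cases arise in respect to vaccination coverage". It then describes three schemes:
- Traditional: controls are people still free of disease, who "are chosen at the end of the cluster/outbreak".
- Case-cohort: controls come from everyone disease-free at the start, so "persons who got the outcome of interest during the cluster/outbreak can be included as controls".
- Density: "Control selection among people still free of the outcome of interest when a case arises forms a density case-control study".

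For all three, section 3.5.11 has one measure of effect: "The vaccine effectiveness will be computed as VE = 1 - OR". Adjustment is by logistic regression, conditional if matched.

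In the cohort part, section 3.4.11 defines crude VE as (1 - RR) x 100. For the adjusted analysis it says "Regression methods could include Cox, Poisson or logistic regression". The choice is to depend on whether incidence is high or low and on the type of denominator, and is to be fixed in study annexes.

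Section 4.6 says that if incidence is high and a traditional case-control design or cohort logistic regression is used, "then the IVE may be overestimated".

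**The concern.** The odds ratio approximates the risk ratio only when the outcome is rare. Section 3.1 looks for clusters where it is not. With a protective vaccine the OR then lies further from 1 than the RR, so 1 - OR exceeds 1 - RR.

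The traditional scheme also conflicts with the representativeness rule in the same section. If the vaccine works and many people fall ill, those still well at the end include a larger share of vaccinees than the source population did.

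In a cohort, logistic regression would place crude VE (1 - RR) and adjusted VE (1 - OR) on different scales. A reader could then take a change of scale for an effect of confounder adjustment.

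The estimate at stake is that of the primary objective. Section 1 says such estimates are meant to inform vaccine recommendations, complementary measures and the handling of vaccine failures.

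**Working it through.** **Inputs.** Attack rate in the unvaccinated, p0: 10% to 50% in Table 2 and 10% to 40% in the rows of Table 3. Risk ratio, RR: 0.4 to 0.6 in Table 2 and 0.3 to 0.6 in the rows of Table 3. Both are cohort tables. Table 6, for case-control studies, gives coverage and OR but no attack rate, so using these values for case-control clusters is an assumption.

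**The protocol's own figure first.** Table 2 gives power 0.45 for p0 = 50%, RR 0.6 and 50 per group. With p1 = 0.3, a two-sided alpha of 0.05 and a continuity correction:
- Corrected difference: 0.2 - 1/50 = 0.18.
- SE under the null: sqrt(2 x 0.4 x 0.6/50) = 0.0980.
- SE under the alternative: sqrt((0.25 + 0.21)/50) = 0.0959.
- z = (0.18 - 1.96 x 0.0980)/0.0959 = -0.126, so power is 0.45, as stated.

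The table is sound and is used here only for its planning values.

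**Overstatement.** With p1 = RR x p0, end-of-outbreak controls or logistic regression on risks give

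OR = RR(1 - p0)/(1 - RR x p0), and the excess of VE is (1 - OR) - (1 - RR) = RR - OR.

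Example: p0 = 0.4, RR 0.5 gives OR = 0.5 x 0.6/0.8 = 0.375. A VE of 50% is reported as 62.5%.

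Reported VE in %, with the excess in points:

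| p0 | RR 0.3 (VE 70) | RR 0.4 (VE 60) | RR 0.5 (VE 50) | RR 0.6 (VE 40) |
|---|---|---|---|---|
| 10% | 72.2 (+2.2) | 62.5 (+2.5) | 52.6 (+2.6) | 42.6 (+2.6) |
| 20% | 74.5 (+4.5) | 65.2 (+5.2) | 55.6 (+5.6) | 45.5 (+5.5) |
| 30% | 76.9 (+6.9) | 68.2 (+8.2) | 58.8 (+8.8) | 48.8 (+8.8) |
| 40% | 79.5 (+9.5) | 71.4 (+11.4) | 62.5 (+12.5) | 52.6 (+12.6) |
| 50% (Table 2 only) | no such row | 75.0 (+15.0) | 66.7 (+16.7) | 57.1 (+17.1) |

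**Control coverage.** Assume 50% coverage in the source population, p0 = 0.4 and RR 0.5. Of the vaccinated, 80% remain well; of the unvaccinated, 60%. Coverage among end-of-outbreak controls is 0.8/(0.8 + 0.6) = 57%, not 50%.

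**The other two schemes**, at p0 = 50%, RR 0.6 and 50% coverage:
- Case-cohort: the vaccinated-to-unvaccinated ratio is (0.5 x 0.3)/(0.5 x 0.5) = 0.6 in cases and 1 in controls. OR = 0.60 and VE = 40%, with no excess.
- Density, matched on time: the OR estimates the rate ratio. Under proportional hazards this is ln(0.7)/ln(0.5) = 0.515, so VE = 48.5%.
- Traditional: VE = 57.1%, which is 17.1 points above 1 - RR and 8.6 points above one minus the rate ratio.

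**The case against.** The strongest reply is that the protocol already knows this. Section 4.6 names high incidence, both affected analyses and the direction of the bias. The document is also a core template: study design, control selection and the cohort model are each left to annexes, and section 3.4.11 ties the cohort model to incidence. No rule imposes end-of-outbreak controls.

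Much of that stands, and the bias cannot be called unrecognised. But section 4.6 gives no size, threshold or restriction. The incidence clause in 3.4.11 does not say which model suits high incidence. In 3.5.11 the measure of effect is fixed whatever the control scheme. An annex could follow every instruction and still overstate VE in exactly the clusters that 3.1 looks for.

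Three stronger readings are tempting and are not supported:
- That 1 - OR is wrong for every permitted scheme. Under case-cohort sampling the OR estimates the risk ratio, and under time-matched density sampling the rate ratio.
- That 17 points is the expected size. It needs a 50% attack rate, found only in Table 2 for cohorts of 50 + 50, whereas section 3.5 is for populations too large to survey or not well defined.
- That density sampling would recover 1 - RR. In the example above it gives 48.5% against 40%.

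**Conclusion.** The point holds for two analyses: traditional end-of-outbreak controls, and logistic ORs from cohorts. Relative to 1 - RR, the excess is about 2 to 3 points at a 10% attack rate in the unvaccinated, 4.5 to 5.6 at 20%, 7 to 9 at 30%, 9.5 to 12.6 at 40% (the Table 3 maximum) and up to 17 at 50%.

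The figures rest on three assumptions: that 1 - RR, the protocol's own cohort definition, is the target; that the cohort tables' attack rates carry over to case-control clusters; and that there is no confounding or misclassification. Against a rate-ratio target, under proportional hazards, the largest excess is about half as great (8.6 points).

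The defect is an acknowledged bias that the methods leave open, although section 3.5.5 already describes control schemes that avoid it. Disclosure in the limitations does not cure this.

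**What to change.** 1. **Section 3.4.11.** For person denominators in high-incidence clusters, replace logistic regression by log-binomial regression or Poisson regression with robust variance, so that adjusted VE is on the same 1 - RR scale as crude VE. The robust variance matters. With 100 per group and attack rates of 40% and 20%, the ordinary Poisson SE of log RR is too large by a factor of sqrt[(1/20 + 1/40)/(0.8/20 + 0.6/40)] = sqrt(0.075/0.055) = 1.17.
2. **Section 3.5.5.** When incidence is high, use case-cohort sampling where a roster of the source population exists and density sampling otherwise. Keep the traditional scheme for low incidence. State the cut-off as a chosen assumption: about 10% in the unvaccinated would hold the excess to roughly 2 to 3 points, but the protocol itself gives no threshold.
3. **Section 3.5.11.** State which ratio the OR estimates under each scheme: risk ratio (case-cohort), rate ratio (density) or odds ratio (traditional). Where only traditional controls exist and p0 is known, report RR = OR/(1 - p0 + p0 x OR) beside 1 - OR, with a reference to 4.6. Check: 0.4286/(0.5 + 0.5 x 0.4286) = 0.60.

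The cost is mainly wording, with the same number of controls and the same questionnaire. There are limits. Case-cohort sampling needs a roster, which an open population may lack, and some controls will also be cases. The conversion needs the attack rate in the unvaccinated, which a line list of cases alone does not supply, and it is only approximate for adjusted ORs. Clusters using density sampling will still be on a rate-ratio scale and should be labelled so.

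### The case-cohort option is given an interval and standard errors for two independent groups, although one person may be both case and control, so its intervals are too wide

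*Protocol*

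**What the plan says.** Section 3.5 covers traditional, case-cohort and density sampling of controls. On the case-cohort option, section 3.5.5 states: "In a case-cohort study, controls are selected from persons who are disease-free at the beginning of the cluster/outbreak". It draws the consequence itself: "persons who got the outcome of interest during the cluster/outbreak can be included as controls".

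Section 3.5.11 then gives a single analysis. The effect measure is fixed as "The vaccine effectiveness will be computed as VE = 1 - OR", and for the interval "An exact 95% confidence interval is computed around the point estimate". For adjustment, "A multivariable (conditional, if matched) logistic regression analysis will be conducted to control for negative and positive confounding", and "Odds ratios and standard errors will be obtained". The only branch is matched against unmatched. Nothing says how a person who appears in both groups enters the interval or the model.

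The cohort part (section 3.4.11) sends the type of multivariable analysis to the study annexes. Section 3.5.11 has no such instruction. The Annex defines Id as unique to each record, not each person, and lists no variable for case, control or subcohort status.

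**The concern.** An ordinary interval for an odds ratio, whether exact or from a logistic model, assumes that cases and controls are separate, independent samples. Under case-cohort sampling they are not. People in both groups make the case and control counts positively correlated, and that correlation reduces the variance of the log ratio. An analysis that ignores it reports more uncertainty than there is.

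Precision is scarce here. Section 4.1 accepts that a cluster often has a small, fixed sample, and section 3.1 looks for clusters with high attack rates, where overlap is largest. Section 4.6 warns that traditional case-control sampling may overestimate effectiveness when incidence is high. That makes the case-cohort option a natural alternative, and it is the one whose interval does not fit.

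**Working it through.** **Inputs.**
- From Table 6 (section 3.5.8, Sample size): alpha 0.05, power 0.80, 50% coverage, OR 0.5 and one control per case give 148 cases and 148 controls.
- Attack rates in the unvaccinated of 10%, 30% and 40% are borrowed from the cohort tables in section 3.4.9. Section 3.5 gives none.
- Assumptions: RR 0.5, 50% coverage, every case enrolled. A closed population of 400 (N1 = N0 = 200) makes the arithmetic concrete. The percentage excess does not depend on 400, because every term scales with 1/N.

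**1. The plan's own figure.** Vaccinated share among cases = 0.5 × 0.5 / (0.5 + 0.5 × 0.5) = 0.333, against 0.5 in controls. The two-sided two-proportion formula gives 136.2 per group. With the continuity correction, (136.17/4) × [1 + √(1 + 4/(136.17 × 0.1667))]² = 147.9, so 148. All 24 rows of Table 6 reproduce to within 1 in this way. The table thus also rests on two independent groups.

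**2. Variance.** Let a, b be vaccinated and unvaccinated cases, and c, d vaccinated and unvaccinated controls.
- Ordinary: V = 1/a + 1/b + 1/c + 1/d.
- About ac/N1 vaccinated people are expected in both groups. Their covariance removes 2 × (ac/N1)/(ac) = 2/N1. The unvaccinated remove 2/N0 likewise.
- True: V − 2/N1 − 2/N0. Excess width on the log scale = √(ordinary/true) − 1.

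The cross-product ratio estimates the RR: (30/60) / (45/45) = 0.5.

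**3. Results** (2/N1 + 2/N0 = 0.02):

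| Attack rate, unvaccinated | Controls per case | a, b | c, d | Ordinary variance | True variance | SE, ordinary v true | Excess |
|---|---|---|---|---|---|---|---|
| 30% | 1 | 30, 60 | 45, 45 | 0.0944 | 0.0744 | 0.307 v 0.273 | 12.6% |
| 40% | 1 | 40, 80 | 60, 60 | 0.0708 | 0.0508 | 0.266 v 0.225 | 18.0% |
| 30% | 2 | 30, 60 | 90, 90 | 0.0722 | 0.0522 | 0.269 v 0.229 | 17.6% |
| 40% | 2 | 40, 80 | 120, 120 | 0.0542 | 0.0342 | 0.233 v 0.185 | 25.9% |
| 10% | 1 | 10, 20 | 15, 15 | 0.2833 | 0.2633 | 0.532 v 0.513 | 3.7% |

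With one control per case, RR 0.3-0.6 and coverage 30-70%, the excess is 9-14% at a 30% attack rate and 12-20% at 40%.

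On the VE scale, the 40%, two-per-case row gives exp(ln 0.5 ± 1.96 × 0.233), a VE interval of 21% to 68%. With the true SE of 0.185 it is 28% to 65%.

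**4. A larger population.** Take 148 cases (49.3 and 98.7) and 148 controls (74 and 74). The ordinary variance is 0.0574.
- From 1000 people, subtract 2/500 + 2/500 = 0.008: √(0.0574/0.0494) − 1 = 7.8%.
- From 2000 people, subtract 0.004: √(0.0574/0.0534) − 1 = 3.7%. Simulation gave 2-3%.

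**5. Simulation** (500 people, 50% coverage, RR 0.5, one or two controls per case). The ratio averaged 0.50 with one control per case. Nominal 95% intervals covered 97-99% (ordinary), 98-99% (conditional exact) and 95% (overlap-corrected). The conditional exact interval was 18-33% wider than the true spread warrants, about 6-7 percentage points beyond the ordinary one.

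**The case against.** The strongest reply is that the dense example is not where the plan mainly uses this design. Section 3.5 turns to case-control or case-cohort sampling when the population is too large to survey or not well defined. The 40%, two-per-case row samples 120 + 240 − 72 = 288 of 400 people, close to a full survey. In a large population the overlap nearly vanishes, as step 4 shows. This stands, and it rules out quoting one range for the excess: a span of 12-26% for attack rates of 30-40% would mix one and two controls per case and assume full case enrolment.

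It can also be said that this is a template, that annexes carry the specifics, and that a person-clustered standard error fits the wording on standard errors. That is partly right for the regression. It does not rescue the exact interval, and the text prescribes one analysis across designs that it has just distinguished.

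Three stronger readings are tempting but unsupported:
- **VE is biased or the type I error inflated.** Neither follows if overlapping people stay in both roles. The error is conservative.
- **The study is underpowered against its plan.** Table 6 uses the same two-group formula, so planned sizes match the planned analysis. The loss is forgone precision.
- **Effectiveness will be exaggerated because overlapping people are dropped from the controls.** Dropping them would matter: at a 40% attack rate a true RR of 0.5 becomes (0.2/0.8)/(0.4/0.6) = 0.375, a VE of 62.5% instead of 50%. But section 3.5.5 allows these people as controls and nothing tells the analyst to remove them. It is a risk left open by silence.

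**Conclusion.** The point holds as a conservative error of modest, variable size. Followed as written, section 3.5.11 gives case-cohort studies intervals that are too wide, because the variance ignores an overlap that section 3.5.5 permits. The direction is certain whenever overlap occurs. The amount is not fixed by the protocol: it ranges from a few per cent, at low attack rates or small sampling fractions, to about a quarter when all cases are enrolled with two controls each at a 40% attack rate in the unvaccinated. Those figures rest on RR 0.5, 50% coverage and attack rates taken from the cohort section. It is worth correcting because the remedy is cheap and the gain is greatest in small clusters with high attack rates.

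**What to change.** Add a case-cohort paragraph to section 3.5.11:
- Subcohort members who become cases are kept in both roles.
- The estimate is reported as VE = 1 − RR.
- The interval and the multivariable standard errors use a variance that accounts for the overlap: a robust variance clustered on person, or a bootstrap that resamples persons. The clustered form uses the observed overlap, so N1 and N0 need not be known.

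Add a person identifier and a subcohort flag to the Annex, since Id is unique only per record. Leave the analysis of traditional and density sampling as it is; nothing here argues against the exact interval or logistic regression for those designs.

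The cost is one paragraph, two variables, slightly more analysis work, and linking the case and control records of the same person.
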